4.4.1 Non-Clinical Efficacy

The preclinical data demonstrating the anti-C5 properties of Zimura™ are described in detail in the Investigator Brochure (IB).

4.4.2 NonClinical Pharmacokinetics of Zimura™

Nonclinical pharmacology studies have been conducted with Zimura™, and, in some cases, with aptamers (Hoehlig et al., 2013). [REDACTED]

[REDACTED]

The safety pharmacology studies did not reveal any effects on cardiovascular, respiratory or neurologic function that would raise concerns for the intended ocular administration.

Further information regarding the pharmacology of Zimura™ is presented in detail in the IB.

4.4.3 Toxicology

[REDACTED]

Additional details of the results of these studies, as well as the results of the various intravenous toxicity studies that were previously conducted, can be found in the IB.

4.5 Clinical Data

4.5.1 Study OPH2000

In a phase 1 ascending dose and parallel group clinical trial the safety, tolerability, and pharmacokinetic profile of multiple intravitreal injections of Zimura™ in combination with Lucentis® 0.5 mg was evaluated in subjects with NVAMD (OPH 2000).

Zimura™ was well-tolerated and no particular safety concerns were identified. No significant evidence of intraocular inflammation, retinal vasculitis, or choroidal vasculopathy was evident. One patient was noted to develop a mild cataract, which was considered to be related to study drug by the investigator; despite this event, the visual acuity improved in this patient during the study.

Visual acuity (VA) assessments were primarily safety assessments to detect any decrease in vision associated with the intravitreal injections. There were no safety issues identified through measurement of VA. Assessment of VA was focused on the treatment-naïve (TN) patient subgroup of 43 patients who had received 6 injections at doses of 0.3 mg, 1 mg or 2 mg. There was a trend towards a mean increase in VA (number of ETDRS letters) from Baseline at all time points for patients in the 0.3, 1 and 2 mg dose groups in the TN subgroup who received 6 injections. At Week 24, there was an improvement in mean VA from Baseline of 13.6 ETDRS letters for the 0.3 mg dose group, 11.7 ETDRS letters for the 1 mg dose group and 15.3 ETDRS letters for the 2 mg dose group.

Fifty-one percent (51%) of patients in the TN subgroup (n=43 patients) gained ≥ 15 ETDRS letters at Week 24. This included 6 patients (46%) in the 0.3 mg dose group, 7 patients (47%) in the 1 mg dose group, and 9 patients (60%) in the 2 mg dose group gaining ≥ 15 ETDRS letters of VA.

4.5.2 Study OPH2001

A separate phase 1 study was also performed in subjects diagnosed with geographic atrophy (GA). In this study, a total of 47 subjects were enrolled, in the 0.3 mg dose arm (n=24) and 1 mg dose arm (n=23). Subjects received treatment with 3 initial intravitreal injections of Zimura™ 0.3 mg/eye or 1 mg/eye, administered at Day 0, Week 4 and Week 8 with a follow up visit at Week 16. Subjects received 2 subsequent injections at Week 24 and Week 36 followed by a final follow up visit at Week 48. Standard safety assessments were performed for ophthalmic variables that included VA, IOP, ophthalmic examination, fundus autofluorescence (FAF), Fluorescein Angiography (FA), and optical coherence tomography (SD-OCT) together with AEs, vital signs and laboratory variables.

Zimura™ was well tolerated and there were no AEs considered to be related to Zimura™. Fifteen subjects (32%) had AEs, predominantly Eye Disorder AEs in the study eye, assessed to be related to the injection procedure. The most frequently reported AEs were conjunctival hemorrhage (4 subjects, 9%), corneal edema (4 subjects, 9%), and dry eye (3 subjects, 6%). No other study eye AEs were reported by more than 2 subjects. The majority of AEs were mild or moderate in severity. There were 2 subjects with AEs of severe intensity: gastrointestinal inflammation and nasopharyngitis.

Five subjects experienced serious adverse events (SAEs), namely device failure, pelvic fracture, angina pectoris, chest pain and gastrointestinal inflammation, but none were related to the study drugs or injection procedure. There were no discontinuations due to AEs.

Vital signs and laboratory assessments did not show any particular clinically significant patterns or changes. Study eye ophthalmic examinations did not indicate any unexpected clinical findings. There were some transient findings post-injection (conjunctiva/sclera and cornea) that resolved prior to the next injection. Vitreous haze was also reported for a few subjects. Intraocular pressure (IOP) showed a small mean increase following injections but no indication of any cumulative increases.

VA assessments did not show any safety signals. VA measurements are not particularly meaningful in GA given the marked irreversible atrophy of neural and supportive tissue and the variable involvement of the macular region. There was suggestion of a drug exposure and dose related slowing of the rate of GA growth during the period of increased frequency of drug exposure (i.e. monthly dosing for 3 months) from Baseline to Week 24, as well as a suggestion of stabilized VA, including VA under low light conditions. The data supported further investigation of Zimura™ in larger clinical trials.

4.5.3 Study OPH2002

The objectives of this study were to evaluate the safety and tolerability of Zimura™ intravitreal injection in combination with VEGF therapy in subjects with idiopathic polypoidal choroidal vasculopathy (IPCV). Subjects included in the study were treatment experienced (prior treatment with anti-VEGF monotherapy of ≥ 8 injections in the previous 12 months) of either gender aged 50 years or above with diagnosis of IPCV. Subjects received 3 monthly intravitreal injections of Zimura™ (1 mg/eye) in combination with intravitreal injection of anti-VEGF agent (Avastin® 1.25 mg/eye or Lucentis® 0.5 mg/eye or Eylea® 2 mg/eye).

Safety endpoints included VA loss (proportion of subjects with > 15 letter loss at Month 30, ophthalmic adverse events (AEs), systemic adverse events (AEs), change in total retinal thickness (SD-OCT) at Month 3, regression and/or elimination of polyps at Month 3 compared to Screening as measured by indocyanine green angiography (ICGA) and laboratory values.

A total of 4 subjects were enrolled in this clinical trial and all the subjects completed the study. None of the subjects had a VA loss of more than 15 ETDRS letters at Month 3. There were no deaths during the study. There was one SAE of endophthalmitis reported in 1 subject. The SAE resolved and was assessed to be related to the injection procedure. None of the ocular AEs were assessed to be related to Zimura™ or anti-VEGF treatment.

The intravitreal administration of Zimura™ in combination with an anti-VEGF agent (Avastin®, Eylea®, or Lucentis®) in patients with IPCV was generally well tolerated. The data supports further investigation of the drug in larger clinical trials.

4.6 Trial Rationale

There is widespread acceptance that the therapeutic benefit of anti-VEGF monotherapy is primarily a result of its potent anti-permeability effects. Studies have shown that VEGF is the most potent inducer of permeability in biologic systems (Dvorak et al., 1995). Multiple investigations of currently available anti-VEGF agents (Lucentis[®], Avastin[®] and Eylea[®]) suggest that they are essentially similar with respect to their safety and efficacy profiles (Brown et al., 2006; Martin et al., 2012; Rosenfeld et al., 2006; Schmidt-Erfurth et al., 2014). Furthermore, the “ceiling” of anti-VEGF mediated therapeutic benefit in NVAMD appears to have been reached as attempts at improving visual outcomes by altering the dose and regimen of anti-VEGF therapy have been unsuccessful (Busbee et al., 2013; Schmidt-Erfurth et al., 2014). Despite maximal therapy with intravitreal monotherapy anti-VEGF agents, the majority of patients do not achieve significant visual gain (≥ 15 ETDRS Letters) or achieve visual acuity of 20/40 or better. In addition, approximately 25% of the patients lose additional vision (Martin et al., 2012). Further, less than monthly regimen results in worse visual outcomes in the real world setting and over time patients in general lose vision with anti-VEGF monotherapy (Rakic et al. 2013, Rasmussen et al., 2013; Rofagha et al, 2013). Approximately one fifth of patients who had received anti-VEGF therapy developed GA within 2 years of treatment (Grunwald et al., 2014). The authors concluded that anti-VEGF therapy may play a role in the development of atrophy. At 5 years, the cumulative incidence was 38%, concluding that the development of GA was common after 5 years of anti-VEGF treatment (Grunwald et al., 2017).

As indicated earlier, there is mounting evidence that both the wet and dry forms of AMD may involve multiple complement pathway proteins. Preclinical laser-induced choroidal neovascularization (CNV) models have implicated complement activation as well. Complement activation has also induced the up-regulation of key mediators of angiogenesis such as VEGF (Nozaki et al., 2006). Evidence for the role of complement in AMD is further reinforced by genetic linkage and association studies that suggest that approximately 50 to 75% of AMD cases have polymorphism in complement regulatory proteins compared to age-matched controls. Furthermore, polymorphism in gene coding for complement or complement regulatory proteins have demonstrated increased risk in AMD (Haines et al., 2005, Edwards et al., 2005, Klein et al., 2005, Hageman et al., 2005, Narayanan et al., 2007). A meta-analysis of 13 published studies proposed that patients who are homozygous for CFH polymorphism Y402H experience a reduced response to anti-VEGF treatment (Chen et al., 2015).

A direct potential relationship between VEGF and CFH was recently demonstrated indicating that VEGF inhibition may lead to a decrease in CFH expression in RPE cells (Keir et al. 2017). Mice that received anti-VEGF treatment, showed a significant decrease in VEGF and CHF. This led to a 200 fold increase in retinal C3 RNA and increased MAC expression suggesting that VEGF inhibition may contribute to complement activation (Keir et al., 2017). Further, in patients with neovascular AMD, aqueous humor samples collected 48 hours after intravitreal injection of bevacizumab demonstrated a decrease in VEGF levels but an increase in C3a, C4a, and C5a levels.

The totality of pre-clinical and genetic related evidence implicates the role of complement activation in AMD. Further, the inhibition of anti-VEGF may contribute further to complement activation by decreasing CFH in RPE cells. Taken together, these findings may potentially indicate that although anti-VEGF treatment has potent anti-permeability characteristics it may also activate the complement cascade by reducing CFH expression and therefore limit the full therapeutic potential of anti-VEGF in NVAMD patients. Hence, a combination treatment which inhibits both VEGF and complement may improve visual outcome and therefore targeting the complement pathway may result in a new therapeutic class in NVAMD.

Zimura™ is currently being developed by Ophthotech Corporation for the treatment of complement mediated retinal diseases including dry AMD, NVAMD. Zimura™ is a PEGylated RNA aptamer and an inhibitor of complement activation. Zimura™ inhibits C5, a central component of the complement cascade, which plays multiple roles in innate immunity and inflammatory diseases. Inhibition of this key step in the complement cascade at the level of C5 prevents the formation of key terminal fragments (C5a and C5b-9) regardless of which pathway (alternate, classical or lectin) induced their generation. The C5a fragment is an important inflammatory activator inducing vascular permeability, recruitment and activation of phagocytes. C5b is involved in the formation of MAC that initiates cell lysis. By inhibiting these C5-mediated inflammatory and MAC activities, additional therapeutic benefit may be achieved in NVAMD patients receiving anti-VEGF monotherapy.

As a dose-response relationship trend in VA gain was evident in Study OPH2000, a higher dose of Zimura 4 mg will be evaluated in this study. Additionally, it has been shown that biweekly intravitreal injections in patients with wet AMD are well tolerated (Rosenfeld et al., 2006, and Stewart et al. 2011). Further, biweekly dosing may increase the trough levels binding activity. Therefore, this study will also evaluate the biweekly

administration of Zimura 2 mg for an induction period of 3 months.

5 TRIAL OBJECTIVES

5.1 Objectives

To assess the safety of intravitreal Zimura™ administered in combination with Lucentis® in treatment naïve subjects with NVAMD.

5.2 Endpoints

Safety endpoints include:

- Adverse events (AEs)
- Vital signs (respiration, heart rate, systolic and diastolic blood pressure, etc.)
- ECG recordings
- Ophthalmic variables (visual acuity, IOP, ophthalmologic examination, stereoscopic fundus photography, fluorescein angiography, and spectral domain optical coherence tomography)
- Laboratory variables (blood: hematology, renal function, hepatic function, and electrolytes; urine: urinalysis)

6 TRIAL DESIGN

There will be 4 dosing cohorts on this trial. Approximately 60 subjects will be enrolled; 10 subjects in cohorts 1 and 2 and 20 subjects in cohorts 3 and 4.

Cohort 1

Administered Day 1 – Month 5, in the following sequence, 2 days apart:

- D0: Lucentis[®] 0.5 mg/eye
- D2: Zimura[™] 4 mg/eye (administered as two injections of Zimura 2 mg/eye)

Cohort 2

Administered Day 1 – Month 5, in the following sequence:

- Lucentis[®] 0.5 mg/eye followed by Zimura[™] 2 mg/eye on the same day

Cohort 3

Induction Phase: Administered Day 1 – Month 2, in the following sequence, 14 days apart:

- D0: Lucentis[®] 0.5 mg/eye followed by Zimura[™] 2 mg/eye on the same day
- D14: Zimura[™] 2 mg/eye

Maintenance Phase: Administered Month 3 – Month 5, in the following sequence:

- Lucentis[®] 0.5 mg/eye followed by Zimura[™] 2 mg/eye on the same day

Cohort 4

Induction Phase: Administered Day 1 – Month 2, in the following sequence, 14 days apart:

- D0: Lucentis[®] 0.5 mg/eye followed by Zimura[™] 2 mg/eye on the same day
- D14: Zimura[™] 2 mg/eye

Maintenance Phase: Administered Month 3 – Month 5, in the following sequence, 2 days apart:

- D0: Zimura[™] 2 mg/eye

- D2: Lucentis® 0.5 mg/eye followed by Zimura™ 2 mg/eye on the same day

All subjects will have a final follow-up visit at Month 6.

The first 10 subjects will be enrolled into Cohort 1 according to the procedures noted below.

The first three subjects will be assigned to Cohort 1 (Lucentis® 0.5 mg and Zimura™ 4 mg). Once the 3rd subject completes a safety period of one week after the first dose of Zimura™ 4 mg without the occurrence of a dose limiting toxicity as defined in Section 9.2.3 Dose Limiting Toxicity, full enrollment of Cohort 1 may commence.

If a DLT occurs in one or more of the first 3 subjects assigned to Cohort 1, then the Ophthotech medical team will evaluate all available data and either discontinue Cohort 1 or enroll an additional three subjects (for a total of 6 subjects) in Cohort 1. If the three additional subjects are enrolled, and no additional DLT occurs once the second set of 3 subjects in Cohort 1 has reached one week after the first dose of Zimura™ 4 mg/eye, full enrollment of Cohort 1 may commence. If one or more DLTs occur in the second set of 3 subjects, a discussion of safety data will be held among the Ophthotech medical team to review the observed toxicities and determine whether Cohort 1 may proceed.

Once Cohort 1 has been fully enrolled, or if enrollment has been stopped due to one or more DLTs, then enrollment in the remaining 3 cohorts may commence. Subjects will be randomized in a 1:2:2 ratio to Cohort 2, Cohort 3, or Cohort 4.

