10.2.3 Day 1 (D2 Visit)

Pre-injection

- Protocol refraction and visual acuity (4 meters) using ETDRS chart (SE)
- Tonometry and Ophthalmologic Examination (SE)

Injection

- Zimura™ 2 mg/eye – **dose 1**
 - Indirect Ophthalmoscopy (SE) – 1 to 2 minutes after the injection to assure that the optic nerve is perfused.
 - Ophthalmologic exam/Tonometry (SE) – After the injection, to confirm perfusion of the optic nerve and return of IOP to ≤ 21 mmHg or within 5 mmHg of pre-injection.
- Zimura™ 2 mg/eye – **dose 2**

Post 2nd Injection

- Indirect Ophthalmoscopy (SE) – 1 to 2 minutes after each injection to assure that the optic nerve is perfused.
- Ophthalmologic exam/Tonometry (SE) – At least 30 minutes after the second injection, a full ophthalmologic exam must be performed and IOP must be < 30 mmHg before the subject leaves the clinic.

3-Day Post-Injection Safety Check (± 1 day)

- Telephone call to subject to ensure there are no signs or symptoms of retinal detachment or endophthalmitis.

10.2.4 Day 9 Visit – Subjects in the DLT cohort only. The DLT cohort is defined as the first 3-6 subjects (depending on if DLTs are noted) enrolled in Cohort 1.

- Vital signs
- Protocol refraction and visual acuity (4 meters) using ETDRS chart (SE)
- Ophthalmologic examination and Goldmann applanation tonometry (SE)
- Spectral Domain optical coherence tomography (SD-OCT) (SE)
- Laboratory tests

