Day 9 will apply to the DLT cohort only. The DLT cohort is defined as the first 3-6 subjects (depending on if DLTs are noted) enrolled in Cohort 1.

Imaging at Day 1 may be repeated if required per section 10.2.1.1 Reconfirmation of Eligibility at Day 1

EW = Early Withdrawal Visit

VISIT WINDOWS: It is essential that subjects adhere to their prescheduled study visits within the specified visit window outlined in section 10.2

D0 = The first day of dosing at each monthly timepoint. D2 = The second day of dosing, 2 days after D0.

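### After expansion of Cohort 1, a second set with no additional DLT opens full 4 mg enrolment whatever the first-set count: 2+0 and 3+0 need no joint review of the six, while 1+1 needs a discussion

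*Protocol*

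**What the plan says.** The rule is in Protocol Section 6 and is repeated in the Synopsis, Sections 9.2.2 and 11.1, and SAP Section 2.2.

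- **After one, two or three first-set DLTs**, the "medical team will evaluate all available data and either discontinue Cohort 1 or enroll an additional three subjects". All three counts follow the same branch.
- **If three are added** and "no additional DLT occurs once the second set of 3 subjects in Cohort 1 has reached one week" after the first 4 mg dose, then "full enrollment of Cohort 1 may commence".
- **If the second set is not clean:** "If one or more DLTs occur in the second set of 3 subjects, a discussion of safety data will be held", and the medical team decides whether the cohort goes on.

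The cohort is planned at ten: "The first 10 subjects will be enrolled into Cohort 1". Protocol Section 4.6 says that "a higher dose of Zimura 4 mg will be evaluated in this study". The highest dose for which Section 4.5.1 gives results from the earlier combination study is 2 mg.

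The extra early safety visit is restricted: "Day 9 will apply to the DLT cohort only" (SAP Section 3.1). Protocol Section 10.2.4 adds: "The DLT cohort is defined as the first 3-6 subjects (depending on if DLTs are noted) enrolled in Cohort 1".

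**The concern.** The second decision asks only whether an additional DLT has occurred. It refers neither to the first-set count nor to the total of six. Two results with the same total, 2+0 and 1+1, are handled differently, and 3+0, with a higher total, needs less review than 1+1.

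This is the last written DLT decision in Cohort 1, and monitoring is lighter after it. The first three to six subjects have a Day 9 visit with visual acuity, eye examination, SD-OCT, vital signs and laboratory tests. After their first 4 mg dose, subjects 7 to 10 have the same-day post-injection checks, a telephone call at about three days, and then Month 1 (±7 days). Their next scheduled laboratory tests are at Month 6. At stake is whether about four more subjects start 4 mg, when a third or a half of the first six have had a DLT, without anyone being required to look at those six together.

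**Working it through.** **The plan's own figure.** There is none to reproduce. Protocol Section 11.4.1 gives no formal sample size calculation, and no section states a target or tolerable DLT rate.

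**Step 1: list the paths.** Counts are subjects with a DLT among subjects 1–3, then 4–6.

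| Path | Total | Required before subjects 7–10 |
|---|---|---|
| 1+0 | 1/6 | first evaluation only |
| 2+0 | 2/6 | first evaluation only |
| 3+0 | 3/6 | first evaluation only |
| 1+1 | 2/6 | first evaluation, then discussion |
| any other path with a second-set DLT | 3/6 or more | first evaluation, then discussion |

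**Step 2: what the first evaluation cannot contain.** It decides whether subjects 4–6 are enrolled, so it has none of their data. If they are dosed after it, it also misses at least 2 days (D0 to D2) + 7 days = 9 days of later follow-up of subjects 1–3.

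**Step 3: how often the path arises.** Assume independent subjects with true DLT rate p, and a team that always expands. With b(k) = C(3,k) p^k (1−p)^(3−k),

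P = P(2+0 or 3+0) = [b(2) + b(3)] × b(0).

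Example at p = 0.20: b(2) + b(3) = 0.096 + 0.008 = 0.104; b(0) = 0.512; P = 0.104 × 0.512 = 0.0532. With ten planned and six enrolled, expected exposure on the path is (10 − 6) × P = 4P.

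| Assumed p | P | 4P (subjects) |
|---|---|---|
| 5% | 0.6% | 0.02 |
| 10% | 2.0% | 0.08 |
| 20% | 5.3% | 0.21 |
| 30% | 7.4% | 0.30 |
| 33% | 7.7% | 0.31 |
| 50% | 6.2% | 0.25 |

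The maximum is 7.7%, at p of about 36%. The 3+0 path alone is p³(1−p)³, at most 1.6% (at p = 50%).

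These are upper bounds, because the team is most likely to discontinue after two or three DLTs in three. If it expands with probability e in those cases, the chance is e × P. At e = 0.5 the maximum is 3.9%.

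**Step 4: what a second look could avoid.** Let r be the share of such discussions that change the decision. Avoided exposure is 4 × P × e × r. At p = 20% and e = 0.5, 4 × 0.0532 × 0.5 = 0.106, which gives 0.01, 0.03 and 0.05 subjects for r = 10%, 25% and 50%. At p = 5% and r = 25% it is 4 × 0.0062 × 0.5 × 0.25 = 0.003.

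**Step 5: 2+0 against 1+1.** P(2+0) = e₂ × 3p²(1−p)⁴ and P(1+1) = e₁ × 9p²(1−p)⁴, where e₁ and e₂ are the chances of expanding after one and two DLTs. With k = e₂/e₁, the 2+0 share of expanded cohorts at exactly 2/6 is 3k/(3k + 9): 25% at k = 1 and 14% at k = 0.5.

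**The case against.** The best defence is that the rule follows new events. Every DLT in the first six subjects leads to a medical-team review. In 2+0 both DLTs were evaluated before expansion and the team chose to go on; in 1+1 the second DLT is new. The only new second-set information in 2+0 is three subjects without a DLT, which is what the expansion was meant to test. This explains much of the asymmetry, and it stands as far as it goes. But the first evaluation answers a narrower question: whether to dose three subjects who will have a Day 9 visit. It does not decide whether to open the cohort to subjects who will not.

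Other safeguards are real. Opening is permissive. The end of Protocol Section 6 allows for Cohort 1 enrolment being stopped for DLTs. Section 10.6 lets the sponsor withdraw subjects, Section 10.7 lets it end the trial, and Section 12.4 brings serious events to it within 24 hours. The trial is open-label. All of this gives power to pause; none of it requires a look at the six together.

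The follow-up argument has limits. The condition of no additional DLT is not expressly confined to subjects 4–6, so it may already cover a late first-set DLT. The visual acuity and cataract criteria in Section 9.2.3.1 run only to Week 1, so later events of those kinds would not count as DLTs.

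A reader might infer that two or three DLTs in six pass with no review, that enrolment must then open, or that the sponsor breaks its own limit of two in six. The documents support none of these. There is a mandatory first evaluation with an option to stop, the wording is permissive, and no cumulative limit is stated. The absence of a Day 9 visit for subjects 7 to 10 is also not caused by this rule: it applies equally after 0 of 3 and after 1+0.

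**Conclusion.** The point holds as a minor one. As written, the second decision ignores the first-set count, so enrolment at 4 mg may open at 2/6 or 3/6 with no required joint review, while 1+1 requires a discussion. The reading of the text is secure. The size rests on assumed DLT rates, independence between subjects, and assumed values of e and r: a path probability of at most 7.7%, about four further subjects, and an avoided exposure that may be near zero. The documents cannot show that a second look would change any decision. The case for making the change is that safety is the trial's only objective and the check uses data already in hand.

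**What to change.** Widen the existing discussion trigger. A discussion of the safety data from all six subjects, to determine whether Cohort 1 may proceed, should be held if there is any second-set DLT (as now) **or** if two or more of the six have had a DLT by that point. Make the same change in the Synopsis, Protocol Sections 6, 9.2.2 and 11.1, and SAP Section 2.2.

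The threshold of two is an addition, since the sponsor's trigger is any second-set DLT. It is chosen because 1+1 already leads to a discussion at that total. Counting all six also brings in a late first-set DLT that raises the total to two, however the no-additional-DLT condition is read. A 1+0 result is handled as before, and the team keeps its discretion. I would not add a mandatory stopping count: the DLT criteria are mixed, and the Grade III–V part of Section 9.2.3.3 does not state that the event must be drug-related.

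The cost is one clause in five places and one short extra discussion on a rare path, with no added subjects, visits or data.
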